Study Objectives	
1. The primary objective is to assess whether the use of a superior hypogastric nerve block performed during uterine artery embolization procedures helps provide better pain management than oral/IV medications alone by assessing patient directed pain scoring and differences in use of oral/IV analgesics
 
2. As secondary objectives the group with the sham procedure and those with the superior hypogastric nerve block will be compared for rate of adverse events, differences in pain/complication related hospital admission/re-admission rates, differences in pain control as related to the bulk volume of fibroids, differences in pain control as related to fibroid disease versus adenomyosis, successful outcome of embolization procedure, successful relief of patient symptoms from the fibroids at time of follow-up

Study Design & Procedure	
This is a prospective double-blinded randomized comparative trial. Experienced interventional radiologists at the MUHC will carry out all intervention.
 
 • 50 consecutive subjects meeting the eligibility criteria, scheduled for uterine artery embolization for symptomatic uterine fibroids and/or adenomyosis. • Consent will be obtained from all patients by a interventional radiologist who will not be involved in the procedure itself. • All procedures will be performed by a qualified interventional radiology medical doctor (IRMD). • Patients who accept to participate and fit the criteria will be randomized to either receive a superior hypogastric nerve block (SHGNB) during the procedure or simply injection of xylocaine in the skin at the periumbilical subcutaneous tissues (sham procedure). • The hypogastric nerve block or sham procedure will be performed by an independent interventional radiologist while the primary operators (radiologists and support staff) of the uterine artery embolization are removed from the room. Once the block or sham procedure is completed, the primary operators returns to the room to

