Because of the success of the group in Ottawa in performing the SHGNB, we have just recently started to offer this procedure as well. Initial results are also very encouraging with recovery nurses informing us that in general the patients seem to be doing much better with the nerve block in place. However the data remains anecdotal. There have been no studies to date comparing simple oral/IV sedation to SHGNB + oral/IV sedation. For this reason, probably, the procedure has been very slow to be adopted by people who perform UAEs. We believe that, to put this issue to rest, there is a necessity for such a comparative trial and, especially important in the context of a subjective outcome such as pain, it is our belief that a randomized double-blinded control trial is needed to obtain conclusive data. This was the reason this study was put together.

2. Research Question:

Is there a difference in subjective pain score patients experience and in the need for analgesics post uterine artery embolization for fibroids if the patients undergo a superior hypogastric nerve block during the embolization procedure.

3. Objectives:

The primary objective is to assess:

- Reduction in subjective pain as measured by patient self administration of visual analogue scale and reduction in use of oral analgesics at home and IV/oral analgesics while in hospital

The secondary objectives are:

- Differences in adverse events between groups with and without SHGNB
- Differences in pain/complication related admissions between groups with and without SHGNB
- Differences in pain in relation to total volume of fibroids between groups with and without SHGNB
- Differences in pain in relation to fibroids vs. adenomyosis between groups with and without SHGNB
- Differences in successful outcome of the embolization both by imaging and clinically between groups with and without SHGNB
- Differences in admission rates
- Differences in rates of return visits to ER for pain issues
- Patient use and appreciation of the online pain survey

4. Implications:

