accordingly. We expect that the data analysis will consist of regression analysis of the temporal pain level distribution between the group with and without the SHGNB. Continuous variable data, with normal distributions, subgroup analysis of the secondary objectives will be compared using a Student's t- test.

▪ **Sample size calculation**

Sample size calculations are based on published data showing the average pain felt by ladies post uterine artery embolization being of 7/10 with a standard deviation of approximately 2.5. The published study of SHGNB for UAE demonstrated a decrease in pain from 7 to 5-2 depending on the analgesics regimen used [6]. We opted for the conservative drop in pain scale from 7 to 5 with a standard deviation of 2.5. This gives an effect size of 0.8. With type I error (alpha) set at 0.05 and type II error (beta) set at 0.2 (power of 80%), the sample size calculations yields a needed sample size of 42. We expect up to a 20% drop out rate due to loss to follow-up, giving a total sample size needed of 50, leaving 25 patients per group. [8]

If the analysis of the data after recruiting 50 patients is highly suggestive of an effect but without statistical significance, and if the calculations suggest we could get statistical significance by doubling the number of participants, and there have been no significant adverse events from the nerve block, we would increase the number of patients to 100. If adverse events have occurred, the number would not be increased unless approval by the ethics committee.

▪ **Interim analysis**

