Data integrity will be maintained throughout the study. Logic rules within the database will be used to maximize integrity, and random data validation checks will be performed routinely. The research investigator will review studies and patients' data on a monthly basis to ensure that patient follow-up is proceeding as expected. All cases where the research investigator finds a discrepancy in imaging interpretation or outcome assessment will be reviewed by the Adjudication Committee, consisting of the principal investigators. An independent radiologist from the MUHC will be asked to determine the outcome of a dispute amongst the Adjudication Committee.

8. Data Analysis:

Data will be collected and tabulated using the commercially available JMP10/SAS statistical analysis software (SAS Institute Inc., Cary, NC, USA). Descriptive statistics will be provided for the efficacy outcome results and will be presented in terms of percentage, frequency, means and 95% confidence interval of the means. Differences between both groups will be compared using the Chi-square test for categorical variables and Student's t- test for the continuous variables. ANOVA test and multivariate logistic-regression analysis will be used to compare interplay of more than two variables. Two-tailed p-values of less than 0.05 will be set for statistical significance.

9. Ethical considerations:

Research Ethics approval from the MUHC Research Ethics Board office will be obtained prior to the commencement of the study or related research procedures. All patients will be informed about the data that will be gathered for the study. All patients will have the ability to refuse participating in the study as soon as they are able to evaluate it and give their approval or not. Patients will always be given options to ask questions at any time and questions will be answered in a non-intimidating way so as to try to avoid influencing the patient's decision. At any time, the patient can decide to remove himself from the study. If this is the case, he will receive the standard of care.

No unique patient identifying data will appear on the sheets that will be coded only by study identification number. A key linking the patient name and study identification number will be maintained in a separate database. All datasheets will be kept in a locked, dedicated research office. All computer records will be maintained in a

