Appendix I

Screening information and selection of cases

Last name: ----- **First name:** -----

Date: -----

Date of Birth: ----- (YY/ MM / DD)

Email address: _____@_____.

RVH/MGH # -----

Assigned ID code: _____ - _____ - _____ (MGH/RVH – Initials – # on envelope)

(Fill ID code out later at time of SHGNB)

INCLUSION CRITERIA	YES	No
Referral for UAE		Exclude
Ability to comply with the requirements of the study procedures.		Exclude
Subject expected to be able to give consent at time of UAE?		Exclude
EXCLUSION CRITERIA		
Patient with abnormal anatomy on MRI in which the aortic/IVC bifurcations are not normally seated and cannot be used to assess the position of the SHGN plexus?	Exclude	
Allergy to local anesthetic agent?	Exclude	
Skin abnormality in the periumbilical region that preclude placement of a needle through this area?	Exclude	
Untreated infection at time of UAE?	Exclude	
History of IBD or Colitis?	Exclude	
Abnormal anticoagulation status?	Exclude	
Pre-existing conditions, which, in the opinion of the investigator, interfere with the conduct of the study?	Exclude	
Uncooperative patient or cannot follow instructions, or who is unlikely to return to get the filter removal due to poor compliance to follow-up medical appointments?	Exclude	
Mental state that can preclude completion of the study?	Exclude	

Pre UAE MRI review:

of fibroids (1/2/3/>3): _____

Size of three largest fibroid – (save image on PACS with fibroids labeled)

1) _____ x _____ x _____ (cm) % necrosis: _____

2) _____ x _____ x _____ (cm) % necrosis: _____

3) _____ x _____ x _____ (cm) % necrosis: _____

% necrosis overall: _____

Adenomyosis: No Yes: Focal Diffuse

Ovarian anastamosis: No

Ovarian anastamosis: No
 Left
 Right

Primary symptom from fibroids:

- Menorrhagia
- Bloating
- Increased urinary frequency
- Constipation
- Dyspaneuria
- Other: _____

Attach Patient's UFS-QOL questionnaire

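### The two effect-modification objectives (fibroid volume; fibroids vs. adenomyosis) have no interaction analysis tied to them, and the only method attached to subgroup analysis is a t-test

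*Combined protocol and SAP*

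**What the plan says.** The synopsis (Study Objectives) lists among the secondary comparisons of sham and block "differences in pain control as related to the bulk volume of fibroids, differences in pain control as related to fibroid disease versus adenomyosis". Section 3 (Objectives) repeats them as "Differences in pain in relation to total volume of fibroids between groups with and without SHGNB" and "Differences in pain in relation to fibroids vs. adenomyosis between groups with and without SHGNB". The synopsis list of efficacy outcomes carries the same two items.

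Three places describe methods that might apply:

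- Section 5, Data gathering and analysis: "Continuous variable data, with normal distributions, subgroup analysis of the secondary objectives will be compared using a" Student's t-test. This is the only sentence in the plan that mentions subgroup analysis.
- Section 8, Data Analysis: "ANOVA test and multivariate logistic-regression analysis will be used to compare interplay of more than two variables". It names no objective, outcome, factor or interaction term.
- The remaining regression statements concern pain over time (section 5) and time-dependent events (synopsis, Statistical Methods). Neither names a modifier.

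On the modifiers themselves, the synopsis admits women with "symptomatic uterine fibroids and/or adenomyosis", so a patient may have both conditions. The pre-UAE MRI review in Appendix I records "Size of three largest fibroid", although the fibroid count may exceed three. It records adenomyosis as no or yes, with focal or diffuse.

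**The concern.** Both objectives are questions about effect modification: is the block-minus-sham difference in pain larger in some women than in others? Answering that requires a contrast of treatment effects, which means an interaction. A t-test between arms within a subgroup, or between subgroups within an arm, does not supply one.

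If the analyst falls back on one t-test per subgroup, the natural way to read the output is to compare p-values. One significant and one non-significant result would then suggest that the block works for one diagnosis or fibroid size and not the other. In a trial of this size that pattern often arises when the effect is identical in both subgroups. What is at stake is a wrong statement about which women benefit from a procedure that the synopsis itself calls semi-invasive.

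The factors are also not defined for analysis. Total volume is the stated objective but only three fibroids are sized, and fibroids versus adenomyosis is not a two-way split when women can have both.

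**Working it through.** **Inputs from the documents.** Difference 2 points (7 to 5), SD 2.5, d = 0.8, 50 patients in two groups of 25, 20% dropout (section 5); two-tailed p < 0.05 (section 8). Completers: 50 x 0.8 = 40, or 20 per arm. The interim look is at 20 completers and the possible extension is to 100 patients (section 5). **Assumed:** how the subgroups split, because the documents give no adenomyosis share and no volume cut-point. I use 10/10, 12/8 and 15/5 per arm, balanced between arms.

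**The plan's own figure.** The plan gives no sample size or power for any subgroup or interaction analysis. Its total of 42 for the main comparison reproduces as a one-sided t-test (21 per arm, power 81.7%). The two-sided test of section 8 would need 26 per arm, or 52. That is a separate matter and is given here only as context.

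**Step 1. Power of a two-sided t-test within one subgroup, d = 0.8 (noncentral t).**

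| n per arm in subgroup | 5 | 8 | 10 | 12 | 15 | 25 |
|---|---|---|---|---|---|---|
| Power | 20.1% | 32.0% | 39.5% | 46.6% | 56.2% | 79.1% |

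**Step 2. Chance that exactly one of two subgroup tests is significant, same true effect in both.** With powers p and q this is p(1 - q) + q(1 - p).

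- 10/10: 2 x 0.395 x 0.605 = 47.8%
- 12/8: 0.466 x 0.680 + 0.320 x 0.534 = 48.8%
- 15/5: 0.562 x 0.799 + 0.201 x 0.438 = 53.7%
- 20 patients, equal split (5/5): 2 x 0.201 x 0.799 = 32.1%
- 100 patients analysed, equal split (25/25): 2 x 0.791 x 0.209 = 33.1%

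A simulated median split on volume at 40 completers, with chance arm balance, gives 47.1%.

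**Step 3. What an interaction test can deliver with 40 completers.** For a two-level modifier with a and b patients per arm, SE in SD units = sqrt(2/a + 2/b), with 36 df and t = 2.028. The 95% CI half-width in points is 2.028 x SE x 2.5. Power is for a 2-point interaction (d = 0.8).

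| Split per arm | SE | Half-width | Power |
|---|---|---|---|
| 10/10 | 0.632 | 3.2 points | 23% |
| 12/8 | 0.646 | 3.3 points | 23% |
| 15/5 | 0.730 | 3.7 points | 19% |

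For continuous volume, the approximate SE of the slope difference per SD of volume is 2 x 2.5/sqrt(40) = 0.79, so the half-width is about 1.6 points. Simulation gives 1.67 (normal volume, assumed) and 1.80 (lognormal, assumed). Power for 1 point per SD is 22% and 19%.

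**Step 4. Cost or gain of one baseline covariate in the main single-score comparison.** With 40 completers and d = 0.8, the unadjusted t-test has 69.3% power. With one covariate the residual variance is multiplied by 1 - R2 and one df is lost; results are averaged over chance imbalance. Power is 68.1, 72.7, 77.6 and 82.8% at R2 = 0, 0.1, 0.2 and 0.3 (assumed). Break-even is at R2 of about 0.03.

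**The case against.** **Section 8 already covers interplay.** These two objectives are the obvious ones involving three variables (pain, arm, modifier), and a two-way ANOVA of pain on arm and adenomyosis would contain the right term. This stands in part: a reader who inferred that the plan has no method capable of testing an interaction would be wrong. But section 8 does not link the ANOVA to these objectives or name the term. Logistic regression does not fit a 0-10 score unless it is dichotomised, and no cut-off is given. Neither method fits continuous volume as a modifier of that score.

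**The misuse is hypothetical.** A reader might infer that the plan commits to a t-test in each subgroup and a comparison of p-values. It does not say so. The sentence in section 5 is garbled and may mean only that continuous secondary outcomes are compared between arms. The rates in step 2 therefore apply to one possible reading, with assumed splits. They also depend on trial size, falling to about one third at 20 or 100 patients with equal splits.

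**Other stronger inferences that fail.** A reader might infer that one significant and one non-significant subgroup is rarer when the effects really differ. That depends on which average effect is held fixed, and the documents give no subgroup effects. A reader might also infer that Appendix I cannot record a woman without fibroids because the printed choices start at 1. The count field has a write-in blank, so zero can be entered.

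**The remedy has low power.** True, at 19-23%. But a wide interval shows the uncertainty, whereas a pair of subgroup p-values conceals it.

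**Conclusion.** The concern holds as a gap in specification. No interaction term or model is tied to the two effect-modification objectives, the one method attached to subgroup analysis does not answer them, and the two modifiers are not defined for analysis. If separate within-subgroup t-tests were used, about 48-54% of trials with 40 completers would show exactly one significant subgroup despite identical effects. This rests on d = 0.8, SD 2.5, a two-sided 5% level and assumed splits of 10/10 to 15/5 per arm.

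It would be wrong to infer that the trial's main result is in doubt. The block-versus-sham comparison does not depend on these analyses, and its unadjusted t-test is valid. These are secondary objectives, and the change should be made because it is cheap and prevents a foreseeable misreading.

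**What to change.** **1. Sections 5 and 8.** Name the main pain score first, since sections 5 and 7.5 list many time points. Then, for these two objectives, replace the subgroup t-test with text such as:

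*For fibroid volume and for adenomyosis, one at a time, the treatment-by-modifier interaction is estimated in a linear model of the main pain score containing treatment, modifier and their product, and reported with a 95% CI. Both analyses are exploratory. Separate subgroup p-values are not used to claim a difference in effect.*

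Define the modifiers:

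- Volume: continuous, computed from the recorded diameters of the three largest fibroids and labelled as a proxy for total volume. Exclude women with adenomyosis only, or show them separately in a sensitivity analysis.
- Adenomyosis: present versus absent on the pre-UAE MRI. Tabulate fibroids only, both, and adenomyosis only, so that the reader can see what the contrast contains.

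Cost: wording only; the diameters and adenomyosis status are already collected. The downside is imprecision, as step 3 of the working shows. The estimates will seldom settle either question.

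**2. Cheap improvement.** Adjust the main single-score pain comparison for start-of-procedure pain, which Appendix II already records before the block, and keep the unadjusted t-test as a sensitivity analysis. This costs about 1 point of power (68.1% against 69.3% with 40 completers) if that score does not predict later pain, and gains power if its R2 exceeds about 0.03. The documents do not show which applies. These figures do not cover the regression over time.

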The previous sample size has been calculated with a conservative number, but the decrease in pain can be as large as from 7 down to 2 based on previous studies. Therefore the above estimation may necessitate more patients than are needed to prove clinical worthiness of the procedure. Clinically, our group feels that we would proceed with the block if we could get at least a 50% decrease in pain from 7 down to 3.5 (a scale of 4 being the common number used for discharge of patients from the recovery room). If a similar sample size calculations is performed for such a drop, a total sample size of 16 would be needed. With a similar drop out rate it is our feeling that an interim analysis should be performed at a patient study completion number of 20, so as to avoid recruiting an excessive number of patients to prove the value of the procedure. Therefore we would perform an interim analysis at 20 patients having completed the study. If the data is statistically significant the study would be terminated early.

6. Study Population

The target population who will be included to participate in this study is all women referred to us for a UAE procedure.

6.1. Inclusion criteria:

1. Women with symptomatic fibroids or adenomyosis that have requested and been approved for uterine artery embolization
2. Women age 35-60 y.o.
3. Ability to comply with the requirements of the study procedures

6.2. Exclusion criteria:

1. Patients in whom the vascular anatomy prevents access to the superior hypogastric nerve plexus safely
2. Patients who have known allergy to the anesthetic agent
3. Patients with signs of skin infection at the entry site of the needle used to place the nerve block
4. Patients with signs of infection such as fever
5. Patients with history of inflammatory bowel disease or with signs of colitis
6. Patients with uncorrectable abnormal coagulation status (INR >1.5 and plt < 50000 without use of anticoagulation agents)
7. Patients with preexisting conditions, which, in the opinion of the investigator, interfere with the conduct of the study.
8. Patients who are uncooperative, cannot follow instructions, or who are unlikely to comply with follow-up appointments or fill-out the post-procedural pain questionnaires.
9. Patients with a mental state that may preclude completion of the study procedure or is unable to provide informed consent

6.3. Randomization:

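### The required total of 42 matches only a one-sided test, but the plan tests two-tailed; with 40 patients left after the allowed dropout, power is about 69%, not 80%.

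*Combined protocol and SAP*

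**What the plan says.** The sample size paragraph in Section 5, repeated in the synopsis under Planned Sample Size, starts from "the average pain felt by ladies post uterine artery embolization being of 7/10 with a standard deviation of approximately 2.5". It then sets the target: "We opted for the conservative drop in pain scale from 7 to 5 with a standard deviation of 2.5", and adds "This gives an effect size of 0.8". With alpha 0.05 and beta 0.2, "the sample size calculations yields a needed sample size of 42". Neither place says whether the calculation is one-sided or two-sided. Up to 20% loss to follow-up is then allowed for, "giving a total sample size needed of 50, leaving 25 patients per group".

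The interim paragraph of Section 5 repeats the exercise for a fall from 7 to 3.5 and reports that "a total sample size of 16 would be needed". The interim look is placed at 20 patients who have completed the study.

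Section 8 (Data Analysis) names Student's t-test for continuous variables and states: "Two-tailed p-values of less than 0.05 will be set for statistical significance". Nothing in the document describes the primary test as one-sided, and the research question in Section 2 asks about a difference without giving a direction.

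**The concern.** An effect size of 0.8 at 80% power and two-sided alpha 0.05 needs more than 42 patients in a two-group t-test, so the calculation and the analysis appear to use different tests. Separately, 50 recruited with 20% lost does not leave 42.

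The error matters most if the result is negative. The study rationale expects the trial to settle the question, and Section 4 says a finding of no benefit would be grounds for not using the block. The type II error drives that decision. If it is nearer 31% than the stated 20%, a non-significant result is weaker evidence against the block than readers will assume.

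**Working it through.** **Inputs (Section 5):** means 7 and 5, SD 2.5, alpha 0.05, power 80%, equal groups, up to 20% dropout, 50 recruited. **Input (Section 8):** two-tailed 0.05, Student's t-test.

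**Effect size.** d = (7 − 5)/2.5 = 0.8, as stated.

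**Method.** Exact power of the two-sample t-test with n per group. The statistic is noncentral t with 2n − 2 degrees of freedom and noncentrality d√(n/2). Power is the probability of passing the critical value, taken at 0.05 in one tail or 0.025 in each tail.

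**Reproducing 42, and testing it two-tailed (d = 0.8):**

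| Evaluable total | n per group | Noncentrality | One-sided power | Two-tailed power |
|---|---|---|---|---|
| 40 | 20 | 2.53 | 79.9% | 69.3% |
| 42 | 21 | 2.59 | 81.7% | 71.6% |
| 50 | 25 | 2.83 | 87.4% | 79.2% |
| 52 | 26 | 2.88 | 88.5% | 80.8% |

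One-sided, 42 is the smallest equal-group total that reaches 80%, an exact match to the plan. Two-tailed, the smallest is 52. A normal approximation does not rescue 42: it gives 40 one-sided and 50 two-tailed.

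**Cross-check on the interim figure.** d = (7 − 3.5)/2.5 = 1.4.

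| Evaluable total | One-sided power | Two-tailed power |
|---|---|---|
| 14 | 79.5% | 67.2% |
| 16 | 84.5% | 74.0% |
| 18 | 88.4% | 79.6% |
| 20 | 91.4% | 84.1% |

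Again the plan's figure, 16, is the one-sided minimum; the two-tailed minimum is 20.

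**Dropout.** 50 × (1 − 0.20) = 40, below 42. To keep 42 after 20% loss, 42/0.80 = 52.5, so 53 must be recruited. Multiplying instead of dividing gives 42 × 1.20 = 50.4, which is close to the stated 50 and may be how it arose. Fifty recruited leaves 42 only if dropout is 1 − 42/50 = 16%.

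**Sources of the shortfall.** Moving from one-sided to two-tailed at 42 evaluable costs 81.7 − 71.6 = 10.1 points. Going from 42 to 40 evaluable costs a further 71.6 − 69.3 = 2.3 points. The sidedness mismatch is therefore the main error.

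**What 40 evaluable can detect.** Solving for 80% two-tailed power at 20 per group gives d = 0.91, that is 0.909 × 2.5 = 2.27 points rather than 2.0.

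**Recruitment for 80% power after 20% loss.** 52/0.80 = 65, or 66 for equal groups.

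**The case against.** The strongest points on the other side are these.

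- **20% is an upper limit.** If the endpoint is recovery-room pain, scored before discharge, few patients would be lost and power would be near 79%. This stands as a reason to report a range, and the plan does not tie the 7-to-5 fall to a time point. But the plan's 80% is meant to hold after its own dropout allowance, and for that comparison the figure is 69%. Even with no dropout, power falls just short of 80%.
- **One-sidedness is inferred.** This is true. It rests on two exact matches, 42 and 16. The shortfall does not depend on the inference: however 42 was obtained, it does not give 80% power under the test in Section 8.
- **The interim look is not underpowered for its target.** It is placed at 20 completers, where two-tailed power for d = 1.4 is 84.1% at 0.05. This stands. The 74.0% at 16 shows that the derivation is wrong; it does not describe the planned look.
- **The trial is not one fixed t-test.** Section 5 also foresees an early look, a conditional extension to 100 patients and regression of pain over time. So 31% is the miss rate of a single-score t-test on 40 patients, not of the whole procedure. None of these features supports the stated 80%, however: the extension is conditional, and no inputs are given for the regression.

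**Conclusion.** The concern holds. The totals of 42 and 16 are one-sided figures in a plan that tests two-tailed; the matching two-tailed totals are 52 and 20. Fifty recruited with 20% lost leaves 40, short of the plan's own 42. Two-tailed power for the 2-point difference is 69.3% at the full dropout allowance and 79.2% with no dropout, against a stated 80%. The type II error at the full allowance is 100 − 69.3 = 30.7%.

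These figures assume the plan's own SD of 2.5, normally distributed scores, equal groups, a t-test on a single pain score, and one analysis at 0.05 with no adjustment for the interim look. The statement must be corrected because it claims a power that the design does not have under its own test.

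**What to change.** Keep 50 patients and correct the text in Section 5 and the synopsis:

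1. State that the calculation is for a two-tailed t-test at 0.05 and that 52 evaluable patients (26 per group) are needed for 80% power at a 2-point difference with SD 2.5.
2. Replace the sentence that derives 50 with a power statement: with 50 recruited, power is about 69% after 20% loss (40 evaluable) and about 79% with none, and with 40 evaluable the difference detectable at 80% power is about 2.3 points. Otherwise the text would require 52 evaluable while recruiting 50.
3. In the interim paragraph, replace 16 with 20. Twenty completers then equals the two-tailed requirement with no dropout margin. Align the synopsis, which treats 20 as already including dropout although it also counts completers; 20 completers at 20% loss means 20/0.80 = 25 recruited.

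The cost is protocol wording and a less favourable power claim, with no extra patients and no change to conduct. If the sponsor prefers to keep 80% power after 20% loss, the alternative is to recruit 66 in equal groups, 16 more than planned.

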
Planned Sample Size
	
Based on published data, the average pain felt by ladies post uterine artery embolization is 7/10 with a standard deviation of approximately 2.5. The published study of SHGNB for UAE demonstrated a decrease in pain from 7 to 2-5 depending on the analgesics regimen used. We

	
opted for the conservative drop in pain scale from 7 to 5 with a standard deviation of 2.5. This gives an effect size of 0.8. With type I error (alpha) set at 0.05 and type II error (beta) set at 0.2 (power of 80%), the sample size calculations yields a needed sample size of 42. We expect up to a 20% drop out rate due to loss to follow-up, giving a total sample size needed of 50, leaving 25 patients per group.
 
Since the pain drop can be more significant than the conservative value we have opted to use, we suggest an interim analysis that would be expected to give us statistical significance if the pain scale was improved by 50% from 7-3.5 (4 being the number usually used by the recovery room to decide to release patients). Based on similar calculations, to show this level of improvement (taking in account a similar drop out rate), one would need a total of 20 patients and therefore we plan on doing an interim analysis at 20 patients having completed the study to see if there is any need to continue the study or not.

Inclusion Criteria	
 1. Women with symptomatic fibroids or adenomyosis that have requested and been approved for uterine artery embolization 2. Age of patients ranging between 35 and 60 years old 3. Ability to comply with the requirements of the study procedures

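### Testing at 20 and again at 50 patients, each at p < 0.05, gives about 8.7% type I error (about 9-11% with the extension to 100), not the stated 5%

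*Combined protocol and SAP*

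**What the plan says.** - **Alpha and size.** Section 5 (Sample size calculation) sets alpha at 0.05 and power at 80% for a drop in pain from 7 to 5 with SD 2.5, and states that "the sample size calculations yields a needed sample size of 42". This is raised to 50 (25 per group) for up to 20% dropout.
- **First look.** Section 5 (Interim analysis) bases a look at 20 completers on a larger drop, from 7 to 3.5, for which it calculates 16 patients. The stopping rule is: "If the data is statistically significant the study would be terminated early". The synopsis (Planned Sample Size) describes the same look as an "interim analysis at 20 patients having completed the study to see if there is any need to continue the study or not".
- **Second look and extension.** Section 5 (Sample size calculation) allows recruitment to go on to 100 under three conditions. The first is: "If the analysis of the data after recruiting 50 patients is highly suggestive of an effect but without statistical significance". The second is a projection that a trial twice as large could reach significance. The third is that the block has caused no significant adverse events; otherwise the ethics committee must approve.
- **Threshold.** Section 8 says: "Two-tailed p-values of less than 0.05 will be set for statistical significance".

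There is no reduced interim level, group-sequential boundary, alpha-spending rule or adjustment for the extension. The extension trigger has no number.

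**The concern.** A test at level 0.05 has a 5% false-positive rate only if it is done once. Here there are two chances to declare success, and a third if the second result is close. A trial that misses at 20 can succeed at 50, and one that narrowly misses at 50 can succeed at 100. The extension is aimed at exactly those trials most likely to cross the line by chance.

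The protocol calls the block semi-invasive and expects this trial to settle whether it should be used. Section 4 says a negative result should spare patients the risks of an unneeded procedure. A false-positive rate close to twice the stated one works against that purpose.

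**Working it through.** **Inputs.** Alpha 0.05, 25 per arm, SD 2.5 and a 2-point drop (Section 5, Sample size calculation); look at 20 completers (Section 5, Interim analysis); two-tailed p < 0.05 and Student's t-test (Section 8); extension to 100 (Section 5). Assumed: one endpoint, equal arms, a pooled test on all patients at each look, and no adverse event blocking the extension.

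**1. The plan's own sample sizes.** Effect sizes are 2/2.5 = 0.8 and 3.5/2.5 = 1.4. For a t-test with 80% power:

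| Effect size | One-sided 0.05 | Two-sided 0.05 |
|---|---|---|
| 0.8 | 20.03 per arm, so 42 in total | 25.52 per arm, so 52 in total |
| 1.4 | 7.10 per arm, so 16 in total | 9.08 per arm, so 20 in total |

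The plan's 42 and 16 both reproduce at one-sided 0.05. The interim figure of 16 therefore uses the full, unadjusted 0.05.

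**2. Two looks, each at two-sided 0.05.** The test statistics at 20 and 50 have correlation sqrt(20/50) = 0.632. With no true effect,

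1 - P(|Z1| < 1.96 and |Z2| < 1.96) = 8.6%.

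A simulation of 1,000,000 null trials with actual t-tests gives 4.98% at the first look and 8.71% over both, so the second look adds 8.71 - 4.98 = 3.73 points. With 42 evaluable at the final look the total is 8.5%; with 40 (50 x 0.8) it is about 8.4%.

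**3. Adding the extension to 100.** The plan's doubling condition implies a trigger. If the observed effect and SD stay the same, doubling N multiplies t by sqrt(2). Significance at 100 needs t = 1.984 (98 df), so the result at 50 must reach 1.984/sqrt(2) = 1.403, which is p = 0.167 on 48 df (0.166 by normal theory). Because the trigger is not stated as a number, a range is shown:

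| Extend if p at 50 is below | Either direction | Only if the trend favours the block |
|---|---|---|
| 0.10 | 9.4% | 9.1% |
| 0.166 | 10.1% | 9.4% |
| 0.20 | 10.3% | 9.5% |
| 0.30 | 10.8% | 9.8% |

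If every non-significant trial were extended in either direction, the figure would be 11.8%.

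**4. False claims in favour of the block only.** Two looks: 8.71/2 = about 4.4%. With the extension at p < 0.166: 10.06/2 = about 5.0%. The corresponding level for a single two-tailed 0.05 test is 2.5%.

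**5. What the interim rule accepts.** With 10 per arm, p < 0.05 needs an observed difference of 2.101 x 2.5 x sqrt(2/10) = 2.35 points. The rule can therefore end the trial on a difference below the 3.5 points that the same section gives as the group's bar for adopting the block.

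**The case against.** Four points deserve an answer.

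- **The intended alpha may be one-sided.** Since 42 and 16 reproduce only at one-sided 0.05, the target could be read as 5% in the favourable direction. Two-tailed 0.05 tests would then give about 4.4% (about 5.0% with the extension), which does not exceed it. But Section 8 states a two-tailed level. If each look were instead tested one-sided at 0.05, two looks would give 8.3%. The mismatch between sizing and analysis is real and should be resolved, but it does not remove the problem.
- **The interim may carry a clinical bar.** The look is introduced with a drop to 3.5. If stopping required both significance and an observed 3.5-point difference, the two-look error would be about 5.1%. The stopping sentence, however, names significance alone.
- **8.7% assumes all 50 are evaluable.** This stands: with the plan's own dropout allowance it is 8.4-8.5%. The conclusion is the same.
- **The extension figures are scenarios.** This also stands. The trigger is unquantified, adverse events can block the extension, and the test at 100 is not described. The two-look figure does not depend on any of this.

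**Conclusion.** The concern holds. Under the plan's own rules the two-sided type I error is 8.7% for looks at 20 and 50 (8.4-8.5% with 40-42 evaluable), and 9.1-10.8% with the extension for triggers from p < 0.10 to p < 0.30. The plan states 5%. The two-look figure follows from applying the only threshold given at both looks. The larger figures also rest on the assumed trigger.

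All figures are for one endpoint and a t-test. The plan joins pain scores and analgesic use in its primary objective and expects regression over time, and it does not say which result the stopping rule applies to. The actual rate could therefore be higher or lower, but repeated testing stays uncorrected under any single test. This should be fixed before the first look.

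**What to change.** **Preferred change.** In Section 5 and the synopsis, stop at 20 completers only if two-tailed p < 0.005, test at 50 at p < 0.047, and delete the extension to 100. In Section 8, state that 0.05 is the overall two-sided level, list the threshold for each look, and name the single endpoint, time point and test to which they apply. Simulated overall error is 4.98%. The exact pair is a matter of choice: 0.002 then 0.049 gives 5.00%, and about 0.028 at both looks also holds 5% by normal theory.

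**If the extension is kept.** Use 0.005 at 20, 0.020 at 50 and 0.034 at 100 on all patients pooled, and fix a numeric trigger before the first look. Even if every non-significant trial is extended, this gives 5.0% (4.98% to 5.02% across simulations). Any actual trigger extends only some of those trials, so the error cannot exceed that. If strictly no more than 5.00% is wanted, round the last level down slightly.

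**Costs.** The change is to protocol wording, but it has consequences for the design:

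- *Early stopping is rarer.* Stopping at 20 falls from 40% to about 11% of trials for a true 2-point drop, and from 84% to 49% for 3.5 points. Overall power at 3.5 points stays above 99%.
- *Power at a 2-point drop, preferred change.* About 78.6% with 50 evaluable and 71% with 42, against 81% and 74% for the two unadjusted looks. A single two-sided test has only 79.2% and about 72%, so most of the shortfall from 80% comes from the one-sided sizing.
- *Power at a 2-point drop, extension kept.* 91% and 86% with a trigger of p < 0.166, or about 89% and 84% if the doubling rule is re-derived for a final level of 0.034 (p < 0.135). The unadjusted extension gives 92% and 88%, partly through inflated alpha. Significance by the 50-patient look falls to 67% and 58%. The chance of extending rises from 11% to 23-25% (from 14% to 28-30% with 42 evaluable).
- *Early estimates remain exaggerated.* For a true 2-point drop, trials stopped at 20 report a mean drop of 3.0 now and 3.7 under the stricter level, though far fewer trials stop there.
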